#### **6.1.1.1 Stopping Rules**

The Sponsor, Investigator (following consultation with the Sponsor), or regulatory officials (regulatory agency or an Institutional Review Board [IRB]/ Independent Ethics Committee [IEC]) have the right to prematurely discontinue or suspend the study or investigational site at their discretion, at any time; if study and/or site conditions warrant. This action may be taken after appropriate consultation among the Sponsor, Investigator, and clinical monitor. The reasons for such action may include, but are not limited to the following:

- Safety concerns, such as more than one third of the patients within a dose cohort have one of the following:

- $\geq$  Grade 3 systemic infusion reactions (despite pre-medication),
- Grade 4 DLTs (Refer to [Section 6.2](#)), or
- Related SAEs (Refer to [Section 8.2.3](#) & [Section 8.3.1.1](#))
- The Investigator does not comply with the protocol, Good Clinical Practice (GCP), and/or any contract between the Investigator and Sponsor, including Contract Research Organizations (CROs) and subsidiaries thereof

In the circumstance of such an event, the Sponsor reserves the right to halt and review this study and will discuss with the Investigator (including the reasons for taking such action) about dose modification, amendment to protocol, or study stopping. Final decision about continuing, termination or any other change in the study would remain with the Sponsor.

### **6.1.2 Part B – Cohort-Expansion**

Up to 57 additional patients with advanced solid tumors that have high Globo H expression (defined as an H-score  $\geq$  100 using a validated IHC assay) will be enrolled in Part B using a Simon's two-stage cohort expansion design. Part B will be conducted to obtain additional safety data, characterize the PK profile of OBI-999, and obtain a preliminary assessment of the clinical activity profile of OBI-999 in Globo H expressing advanced solid tumors.

Patients enrolled in Part B will receive the RP2D dose of 1.2 mg/kg (capping calculations at a maximum of 100 kg) OBI-999 on Day 1 of each 21-day cycle.

The following 3 cohorts of patients who have high expression of Globo H by a qualified laboratory assessment (Globo H H-score  $\geq$  100 using a validated IHC assay) will be enrolled in Part B.

- Cohort 1: Pancreatic cancer
- Cohort 2: Colorectal cancer
- Cohort 3: Basket (any solid tumor type other than those included in Cohorts 1 and 2)

Patients will continue to receive treatment with OBI-999 until disease progression, unacceptable toxicity, consent withdrawal, or for up to 35 cycles (approximately 2 years), whichever occurs first.

### **6.1.3 Duration of Study**

The study (Parts A and B) will include a screening period (up to 28 days), a treatment period, and a follow-up period.

Patients will continue to receive treatment with OBI-999 until disease progression, unacceptable toxicity, consent withdrawal, or for up to 35 cycles (approximately 2 years), whichever occurs first. Patients will be followed up to the 24-week scheduled response assessment for the purposes of counting objective responses for Simon's two-stage design success criteria.

The safety follow-up visit will be conducted 28 days after the last dose of study treatment.

## 6.2 Definition of Dose-Limiting Toxicities (Part A only)

A DLT is defined as the occurrence of any of the following events, within the first cycle of treatment that is considered to be at least possibly related to OBI-999:

- Grade 4 neutropenia lasting more than 7 days.
- Febrile neutropenia.
- Grade 4 thrombocytopenia.
- Grade 3 thrombocytopenia with  $\geq$  Grade 2 bleeding requiring platelet transfusions.
- Grade 3 fatigue, nausea and vomiting or diarrhea that does not resolve to Grade 1 or Baseline within 72 hours despite optimal supportive care.
- Any Grade 4 gastrointestinal (GI) toxicity.
- Any other Grade 3 or Grade 4 non-hematological toxicity (except Grade 3 fatigue, nausea, vomiting, or diarrhea lasting  $<24$  hours with optimal therapy, Grade 3 non-hematologic laboratory abnormalities that resolve to Grade 1 or Baseline within 14 days).

All AEs unless they are determined to be not related to study drug will be taken into consideration in determining DLTs. NCI CTCAE version 5.0 will be the basis for the descriptive terminology and grading of AEs. The period for DLT observation is 21 days from the start of first dose of OBI-999 (i.e., Day 1).

## 6.3 Discussion of Study Design

This study will be undertaken in patients with advanced cancer that has progressed on prior therapy. In this setting, patients will be seeking to alleviate symptoms of their fatal disease and prolong life through exposure to a novel agent.

Patient safety, and a favorable risk/benefit balance, will be carefully monitored throughout and after treatment. Additionally, attention will be taken to enroll only patients who are felt to be in sufficient condition to undertake this clinical trial, as defined by adequate performance status, suitable baseline organ function, and the Investigator's determination that there are no significant comorbid conditions which present undue risk. Nevertheless, unexpected toxicity of the investigational drug may occur, and all patients will have informed consent prior to treatment.

# 7 Selection and Withdrawal of Patients

## 7.1 Inclusion and Exclusion Criteria

### 7.1.1 Inclusion Criteria

Patients must meet all of the following criteria in order to be included in the study (for both Parts A and B unless specified otherwise):

1. Male or female patients, 18 years of age or older at the time of consent.
2. Provide written informed consent prior to performing any study-related procedure.
3. Histologically or cytologically confirmed patients with advanced solid tumors.

4. Patients must have been treated with established standard-of-care therapy, or physicians have determined that such established therapy is not sufficiently efficacious, or patients have declined to receive standard-of-care therapy. In the latter case, the informed consent must state the effective therapies the patient is declining.
5. Measurable disease (i.e., at least one measurable lesion per RECIST 1.1) ([Eisenhauer, et al., 2009](#)).
6. Eastern Cooperative Oncology Group (ECOG) performance status of 0 or 1 ([Oken, et al., 1982](#)).
7. Adequate organ function defined as:
  - a. Hepatic:
    - i. Serum ALT  $\leq 3 \times$  upper limit of normal (ULN),  $\leq 5 \times$  ULN in the presence of liver metastases
    - ii. Serum AST  $\leq 3 \times$  ULN,  $\leq 5 \times$  ULN in presence of liver metastases
    - iii. Serum bilirubin  $\leq 1.5 \times$  ULN (unless due to Gilbert's syndrome or hemolysis)
  - b. Renal:
    - i. Creatinine clearance  $> 50$  mL/minute using Cockcroft Gault equation
  - c. Hematologic:
    - i. Absolute neutrophil count  $\geq 1,500/\mu\text{L}$
    - ii. Platelets  $\geq 100,000/\mu\text{L}$
    - iii. Hemoglobin  $\geq 8 \text{ g/dL}$
8. Patient is willing and able to comply with all protocol-required assessments, visits, and procedures, including a pretreatment tumor biopsy. Archival tumor biopsies are acceptable at baseline.
9. Females of childbearing potential must have negative serum pregnancy test prior to starting study therapy, and agree to use a reliable form of contraceptive during the study treatment period and for at least 120 days following the last dose of study drug.  
Patient not of childbearing potential (i.e., permanently sterilized, postmenopausal) can be included in study. Postmenopausal is defined as 12 months with no menses without an alternative medical cause.  
Male patients must agree to use an adequate method of contraception during the study treatment period and for at least 120 days following the last dose of study drug.
10. Cannot be breast feeding.
11. Patients with human immunodeficiency virus (HIV) infection are eligible if CD4+ T-cell counts  $\geq 350 \text{ cells}/\mu\text{L}$ ; patients on antiretroviral therapy (ART) should be on an established dose for at least 4 weeks and have an HIV viral load less than 400 copies/mL prior to enrollment.
12. Patients with serological evidence of chronic hepatitis B virus (HBV) infection are eligible if they have an HBV viral load below the limit of quantification with or without concurrent viral suppressive therapy.
13. Patients with a history of hepatitis C virus (HCV) infection should have completed curative antiviral treatment and have a viral load below the limit of quantification.

14. Patients in Part B (Cohort-Expansion) must have documented Globo H H-score  $\geq 100$  from a qualified laboratory IHC assay in one of the following tumor types to be enrolled in the respective cohort:

- Cohort 1: Pancreatic cancer
  - Histopathologically confirmed patients with metastatic adenocarcinoma of the pancreas.
- Cohort 2: Colorectal cancer
  - Histopathologically confirmed patients with metastatic colorectal adenocarcinoma.
- Cohort 3: Basket (any solid tumor type other than those included in Cohorts 1 and 2)
  - Histologically or cytologically confirmed patients with advanced solid tumors.

### **7.1.2 Exclusion Criteria**

Patients meeting any of the following criteria are ineligible to participate in this study:

1. Less than 3 weeks from prior cytotoxic chemotherapy or radiation therapy; and less than 5 half-lives or 3 weeks, whichever is shorter, from prior biologic therapies, prior to the first dose of OBI-999.
2. Has undergone a major surgical procedure (as defined by the Investigator) or significant traumatic injury within 28 days prior to the first dose of OBI-999.
3. Sensory or motor neuropathy of Grade 2 or greater.
4. Patients with a history of solid organ transplant.
5. Unresolved toxicities from prior anticancer therapy, defined as having not resolved to Grade 0 or 1 (using NCI CTCAE version 5.0), except for alopecia and laboratory values listed in the inclusion criteria.
6. Receipt of any prior therapy targeting Globo H.
7. Known hypersensitivity to OBI-999 or its excipients.
8. Has known untreated central nervous system metastases. Patients with treated brain metastases are eligible if there is no evidence of progression for at least 4 weeks after CNS-directed treatment, as ascertained by clinical examination and brain imaging (magnetic resonance imaging [MRI] or computed tomography [CT]) during the screening period.
9. Has significant clinical cardiac abnormality (e.g., clinical heart failure or unstable angina).
10. Any medical co-morbidity that is life-threatening or, in the opinion of the Investigator, renders the patient unsuitable for participation in a clinical trial due to possible noncompliance, would place the patient at an unacceptable risk and/or potential to affect interpretation of results of the study.
11. Is receiving any concurrent prohibited medication as listed in [Section 8.6.3](#).

## 7.2 Treatment Discontinuation and Withdrawal of Patients

A patient who withdraws from the study within the DLT evaluation period for reasons other than drug related AE will be replaced.

A patient may voluntarily withdraw or be withdrawn from the study treatment at any time for reasons including, but not limited to, the following:

- Progressive disease.
- Grade 4 infusion reactions and OBI-999-related toxicity.
- Dose reductions required on more than 2 occasions for toxicity related to OBI-999.
- Treatment interruption for more than 2 consecutive doses for related or unrelated reasons.
- Patient withdrawal of consent: At any time, a patient's participation in the study may be terminated at his/her request or on the basis of the Investigator's clinical judgment.
- Inter-current illness: A condition, injury, or disease unrelated to the primary diagnosis that becomes apparent during treatment and necessitated the patient's termination from the study.
- General or specific changes in the patient's condition that renders him/her ineligible for further treatment according to the inclusion/exclusion criteria.
- Protocol deviation: The patient's findings or conduct fail to meet the protocol entry criteria or fail to adhere to the protocol requirements (e.g., drug noncompliance, failure to return for defined number of visits) such that the Sponsor and the Investigator agree that the deviation necessitates premature termination from the study.
- Lost to follow-up: The patient stops coming for visits, and study personnel are unable to contact the patient.

## 7.3 Follow-Up for Drug Discontinuation/Patient Withdrawal from Study

If a patient discontinues study treatment and is withdrawn from the study for any reason, the study site must immediately notify the Sponsor. The date and the reason for study treatment discontinuation / study withdrawal must be recorded on the electronic case report form (eCRF). Patients who withdraw prematurely are to attend an early termination visit, if possible, and complete all assessments.

In the event that a patient discontinues prematurely from the study due to a treatment-emergent adverse event (TEAE) or serious TEAE, the TEAE or serious TEAE will be followed until it resolves (returns to normal or baseline values) or stabilizes, or until it is judged by the Investigator to be no longer clinically significant.

Once a patient is withdrawn from the study, the patient may not re-enter the study.

## 8 Treatments

### 8.1 Details of Study Treatment

OBI-999 is an ADC composed of a Globo H-targeting humanized IgG1 mAb (OBI-888; IND #136,961), which is covalently linked to MMAE by a cathepsin B protease cleavable linker. Globo H is a TACA.

OBI-999 drug product (DP) liquid is packaged in a single-use 10 mL transparent borosilicate type 1 glass vial for IV infusion. Each vial of OBI-999 DP liquid contains 5 mL of 5 mg/mL OBI-999 drug substance (DS) in a pH 6.0 solution formulated with 25 mM sodium citrate, 150 mM Arginine, and 0.02 % (w/v) Polysorbate 80. OBI-999 DP is diluted to the appropriate concentration in 0.9 % sodium chloride or 5% glucose prior to administration by IV infusion.

All study drug will be supplied by OBI Pharma Inc., and must remain under adequate security and proper storage conditions. Do not use study drug after the expiration date, which is imprinted on the drug container.

The OBI-999 DP should be administered to the study subjects within 4 hours of reconstitution at room temperature. Overall storage of the DP material should not exceed 8 hours at room temperature. Refer to [Appendix 1](#) for details of dispensing, volume needed, mixing and reconstitution of OBI-999.

#### 8.1.1 Packaging and Labeling

OBI-999 drug product will be packaged in carton boxes. Each box will contain ten OBI-999 vials. The labels on each kit will meet the applicable regulatory requirements for each country.

OBI-999 will be packaged and labeled according to current Good Manufacturing Practices (GMP) guidelines. Details of the packaging and labeling are provided in the Pharmacy Manual.

#### 8.1.2 Storage

OBI-999 drug product must be stored at a temperature of 2 to 8°C.

## 8.2 Treatment Regimen

### 8.2.1 OBI-999 Doses

For Part A (Dose-Escalation), OBI-999 was planned to be given at doses of 0.4, 0.8, 1.2, 1.6, and 2.0 mg/kg (capping calculations at a maximum of 100 kg) using a 3+3 design to identify the MTD and RP2D.

For Part B (Cohort-Expansion), OBI-999 will be given at the RP2D of 1.2 mg/kg (capping administered dose to a maximum of 120 mg for 100 kg).

### 8.2.2 OBI-999 Administration

OBI-999 investigational drug solution (OBI-999 drug product mixed with saline/glucose infusion solution) will be administered on Day 1 of each 21-day cycle by the site staff. The infusion should be given for a duration of approximately 60 minutes ( $\pm$  10 minutes), for the initial 2 cycles (Cycle 1 and Cycle 2). The infusion duration for Cycles 3 and beyond may be reduced, at the Investigator's discretion, to 30 minutes if no infusion related AEs occur during the first 2 cycles.

Treatment will continue until disease progression, unacceptable toxicity, consent withdrawal, or for up to 35 cycles (approximately 2 years), whichever occurs first.

### **8.2.3 Prophylactic Measures**

Approximately 30 to 60 minutes prior to OBI-999 administration, all patients should receive prophylactic treatment for infusion reactions. Prophylactic treatments include acetaminophen orally and diphenhydramine (or equivalent) orally or IV (recommended doses are: acetaminophen 650 mg, diphenhydramine 50 mg). If an alternative premedication regimen is thought to be required, Sponsor approval should be sought.

For patients who experience an infusion reaction despite initial premedication, additional prophylactic treatment may be added prior to subsequent doses, including an H2 blocker such as ranitidine, and/or corticosteroids.

Prophylactic treatment for infusion reactions may be withheld at the Investigator's discretion if no infusion reactions were observed with the first cycle of treatment. Additional details are provided in [Section 8.3.1.1](#).

## **8.3 Dose Modifications and Toxicity Management**

Escalation to a higher OBI-999 dose cohort is not permitted during the study.

Dose modifications for hematologic toxicity, non-hematologic toxicity, and infusion reactions should be independently assessed at each visit. Recommendations for dose modifications for toxicity are provided in Table 8-1.

**Table 8-1 OBI-999 Dose Modifications for Toxicity**

Toxicity	Hold Dose	% of Full Dose after Recovery to Grade 0-1
Grade 1	Do not hold dose	100
Grade 2	Hold dose until resolution to Grade 0 or 1	75
Grade 3	Hold dose until resolution to Grade 0 or 1	75
Grade 4	Treatment should be discontinued	Not applicable

Once the dose has been reduced for toxicity and found to be well tolerated, re-escalation may be permitted at the Investigator's discretion. If a patient requires dose reductions on more than 2 occasions for toxicity related to OBI-999, the patient should discontinue from the study.

All reasons for treatment modifications should be fully explained.

The study drug dose which is not administered within the permitted window period of  $\pm 3$  days, must be skipped, and the next dose will be administered as per protocol schedule. Any skipped dose due to safety reason and if medically justified, for OBI-999 treatment related or unrelated reasons, will not be captured as a protocol deviation for this study.

Treatment interruption for more than 2 consecutive doses for related or unrelated reasons may necessitate discontinuation of study treatment.

Treatment interruption for intercurrent non-treatment related AEs will be at the Investigator's discretion and based on the well-being of the patient. All reasons for treatment interruption and

delays should be fully explained. Treatment for hematologic and non-hematologic toxicity may be implemented as clinically indicated according to institutional guidelines. Refer Table 8-2 for therapeutic antiemetic and anti-diarrheal recommendations.

**Table 8-2 Therapeutic Antiemetic and Anti-Diarrheal Recommendations**

Diarrhea and Abdominal Cramping	Nausea, Vomiting, or Anorexia
Dicyclomine: Recommended when the predominant issue is cramping or abdominal pain	1st line: 5HT3-inhibitors
Diphenoxylate/Atropine or/and Loperamide	2nd-line: Dexamethasone, ideally in combination with a 5HT3-inhibitor. Short term use can be very effective Other agents: anti-histamines; benzodiazepines; proton pump inhibitors; dopamine antagonists; cannabinoids
Hyoscine: Anti spasmodic agents helpful for abdominal cramping	
Budesonide (Entocort EC): Corticosteroid with limited systemic absorption; 9 mg once daily for up to 8-12 weeks	

### 8.3.1 Infusion Reactions

Signs/symptoms of infusion reactions may include: allergic reaction/hypersensitivity (including drug fever); arthralgia (joint pain); bronchospasm; cough; dizziness; dyspnea (shortness of breath); fatigue (asthenia, lethargy, malaise); headache; hypertension; hypotension; myalgia (muscle pain); nausea; pruritic/itching; rash/ desquamation; rigors/chills; sweating (diaphoresis); tachycardia; tumor pain (onset or exacerbation of tumor pain due to treatment); urticaria (hives, welts, wheals); and vomiting.

In the event of an infusion reaction, additional serum/plasma samples may be drawn at the time of the event to evaluate drug concentration and ADA, as well as to assess levels of cytokines and/or other markers of inflammation.

#### 8.3.1.1 Management of Infusion Reactions

As stated in [Section 8.2.3](#) all patients will receive prophylaxis prior to the first dose of treatment. If no infusion reactions occur with prophylactic treatments, these may be withheld for subsequent doses at the Investigator's discretion. Prophylactic treatment as described in [Section 8.2.3](#) should be resumed for all future doses if subsequent dosing without prophylaxis is associated with infusion reactions.

In the event of an infusion reaction, the OBI-999 infusion should be interrupted and medical therapy administered according to institutional standard of care.

Patients who experience a Grade 1 or Grade 2 infusion reaction may resume the infusion of drug at a reduced infusion rate (30% to 50% slower than initial rate) on the same day following appropriate medical management, as long as this falls within the 4-hour drug administration window (see [Section 8.1](#) and [Appendix 1](#)). If the 4-hour window from product reconstitution is exceeded, new drug may be prepared to administer the remainder of the planned dose.

Patients who experience a Grade 3 infusion reaction may be retreated at the discretion of the Investigator at the next scheduled treatment. Such patients should receive additional premedication that may include an acetaminophen, an antihistamine, or a corticosteroid.

Patients should be followed for at least 4 hours and until resolution of the infusion reaction. In person or telephonic follow up the next day should also be arranged to ensure there are no recurrent symptoms. Patients should also be instructed to contact study personnel if symptoms recur at later time points.

OBI-999 should be permanently discontinued in patients who experience a life-threatening (Grade 4) infusion reaction.

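### For a Grade 2 infusion reaction, Protocol Table 8-1 and Section 8.3.1.1 give different instructions on holding and on dose, and neither says which prevails

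*Protocol*

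**What the plan says.** Protocol Section 8.3 opens with the scope: "Dose modifications for hematologic toxicity, non-hematologic toxicity, and infusion reactions should be independently assessed at each visit". It continues: "Recommendations for dose modifications for toxicity are provided in Table 8-1". Infusion reactions are not excepted.

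Table 8-1 is organised by grade alone. For both Grade 2 and Grade 3 the action is "Hold dose until resolution to Grade 0 or 1", and the column giving the percentage "of Full Dose after Recovery to Grade 0-1" shows 75. Grade 1 is not held and stays at 100. Grade 4 ends treatment.

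Section 8.3.1.1 has its own instructions. Any infusion reaction interrupts the infusion. After Grade 1 or 2 the patient "may resume the infusion of drug at a reduced infusion rate (30% to 50% slower than initial rate) on the same day", following medical management. If the four-hour limit on prepared drug is passed, "new drug may be prepared to administer the remainder of the planned dose". For Grade 3, "Patients who experience a Grade 3 infusion reaction may be retreated at the discretion of the Investigator at the next scheduled treatment", with added premedication. For Grade 4, "OBI-999 should be permanently discontinued in patients who experience a life-threatening (Grade 4) infusion reaction".

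The text below Table 8-1 adds that a patient who needs dose reductions for drug-related toxicity on more than 2 occasions should discontinue. Section 7.2 lists the same event among the reasons for withdrawal.

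**The concern.** At Grade 2 the two places give different instructions for the same event. One holds and restarts at a reduced dose. The other resumes the same day, lowers only the rate and lets the planned amount be completed. Two sites could each follow the protocol and give different doses.

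Three things could be affected. The first is exposure at the recommended dose, which Part B is meant to characterise. The second is time on treatment: a restart at 75% for a drug-related reaction is a dose reduction and counts toward the more-than-2 rule, whereas a slowed infusion apparently does not. The third is the Safety Review Committee's task in Sections 6.1 and 14.6 of judging whether the dose modification rules work, which is hard if one rule can be read in two ways.

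**Working it through.** **Inputs.** Part B dose of 1.2 mg/kg, capped at 120 mg for 100 kg (Protocol Section 8.2.1); 75% after Grade 2 or 3 (Table 8-1); the Section 8.3.1.1 instructions by grade. The 70 kg weight is an assumption, used for illustration.

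**Step 1: the stated cap.** 1.2 mg/kg × 100 kg = 120 mg, which agrees with Section 8.2.1.

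**Step 2: the two sources by grade.**

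| Grade | Table 8-1 | Section 8.3.1.1 | Comparison |
|---|---|---|---|
| 1 | No hold, 100% | Interrupt; may resume the same day, more slowly | Wording differs; both lead to 100% |
| 2 | Hold to Grade 0–1, then 75% | Interrupt; may resume the same day, more slowly; remainder of planned dose | Conflict on holding and on amount |
| 3 | Hold to Grade 0–1, then 75% | May be retreated at next scheduled treatment; no dose named | Unclear whether 75% applies |
| 4 | Discontinue | Discontinue | Agree |

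On timing at Grade 2, a reaction that settles to Grade 0 or 1 within hours could satisfy both sources. Section 8.3.1.1 does not require that recovery, however, only medical management. On amount, the two cannot both apply to the same administration: one gives 75% of full dose, the other the rest of the planned dose.

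**Step 3: size at Grade 2, for a patient on full dose.**

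- Reduced dose per kg: 0.75 × 1.2 = 0.9 mg/kg.
- At the cap: 120 mg against 0.75 × 120 = 90 mg, a difference of 30 mg.
- At an assumed 70 kg: 1.2 × 70 = 84 mg against 0.75 × 84 = 63 mg, a difference of 21 mg.

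No such comparison can be made at Grade 3, because Section 8.3.1.1 gives no figure.

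**Step 4: the next scheduled dose after Grade 2.** Section 8.3.1.1 deals with the infusion in progress and is silent on the dose at the next cycle. If Table 8-1 applies there, it is 75%. If Section 8.3.1.1 alone governs infusion reactions, no dose is stated.

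**Step 5: is there a rule of precedence?** None is stated. Section 8.3.2.1, on neuropathy, cites Table 8-1 for its 75% restart. Section 8.3.1.1 neither cites the table nor sets it aside.

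**The case against.** The best defence is that the two places govern different acts. Section 8.3 speaks of assessment at each visit, and the table gives a dose after recovery; both suit scheduled doses. Section 8.3.1.1 handles an infusion already running. On that reading a Grade 2 patient finishes today's dose at a slower rate and Table 8-1 sets the next one. A second defence is that the specific subsection displaces the general table, and that the absence of a cross-reference, in contrast to the neuropathy subsection, shows this. The language is also soft: the table is offered as recommendations, and resumption is permitted, not required.

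These readings are reasonable, and either would narrow the conflict. But the protocol states neither, and they lead to different next-cycle doses: 75% under the first, unstated under the second. Soft wording does not help, since it leaves both courses compliant.

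A reader might infer more than the documents support. One inference is that Section 8.3.1.1 continues the full dose at Grade 3 as well. It does not: same-day resumption and the remainder of the planned dose belong to the Grade 1 or 2 paragraph, and the Grade 3 sentence can coexist with 75%. Another is that the 25% gap carries through all later cycles. That rests on silence about later doses, and the text below Table 8-1 permits re-escalation. A third is that the sources disagree at every grade but 4; at Grade 1 both lead to 100%.

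It also stands that the practical impact is unknown. The documents give no frequency of infusion reactions, and Section 8.2.3 calls for premedication in all patients at the start.

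**Conclusion.** The protocol contradicts itself for Grade 2 infusion reactions, on whether to hold and on how much to give. At Grade 3, and for the next scheduled dose after Grade 2, Section 8.3.1.1 leaves the dose unstated, so it is unclear whether Table 8-1 applies. Grade 1 differs only in wording, and Grade 4 agrees.

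At Grade 2 the readings differ by a quarter of the full dose for a patient on full dose. They may also differ by one occasion per drug-related reaction under the more-than-2 rule. This rests on reading Section 8.3's reference to Table 8-1 as covering infusion reactions, which its preceding sentence supports. Exposure, time on treatment and the tolerability summary could be affected; by how much cannot be judged from the documents. No view is taken on which clinical rule is right.

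**What to change.** Reconcile Section 8.3, Table 8-1 and Section 8.3.1.1:

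- State which passage governs infusion reactions at each grade, separately for the interrupted infusion and for the next scheduled dose. The content of the rule is for the sponsor and the Safety Review Committee.
- State whether a slowed or interrupted infusion counts as a dose reduction under the more-than-2 rule.

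In the protocol this takes a clarifying sentence and a table footnote, with no added patients or procedures. It applies to any further use of this text, because SAP Section 3 records that the sponsor stopped the study on 10 November 2023 and an amendment cannot change doses already given.

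The abbreviated report should therefore also state which rule sites applied to infusion reactions. SAP Section 11 keeps the listing of all study drug administration data, so the affected administrations can be looked up there. The cost is a short check of that listing and a sentence or two of text.
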